9.7.2.2 Secondary endpoints

The secondary endpoints cover the following five types of assessments:

- 1. All serious adverse events
- 2. All medical events of special interest
- 3. All medication errors and near medication errors
- 4. Use of rFXIII other than for prophylactic treatment.
- 5. Annualised bleeding rate

The first three secondary endpoints will be presented for all patients as well as by special populations, comprising children, elderly, pregnant and lactating women, and patients with renal insufficiency.

All the secondary endpoints will be collected from first study related activity after signing the informed consent to the end of patient's participation in the study, expected to last a maximum of 6 years.

Study ID: NN1841-3868 UTN: U1111-1131-1558 EU PAS No.: ENCEPP/SDPP/3687

 Date:
 02 February 2016

 Version:
 2.0

 Status:
 Final

 Page:
 46 of 65

Serious adverse events

Serious adverse events will be summarised, displaying the number of events and the number and percent of patients experiencing the reaction by MedDRA preferred term.

Serious adverse events will further be listed with patient ID, site, age, preferred term, date of first dose, date of onset, date of arrest, severity, if it is serious or not, relationship to study drug, action, and outcome.

Medical events of special interest

Medical events of special interest will be summarised, displaying the number of events and the number and percent of patients experiencing the reaction by MedDRA preferred term.

Medical events of special interest will further be listed with patient ID, site, age, preferred term, date of first dose, date of onset, date of arrest, severity, seriousness, relationship to study drug, action, and outcome.

Medication errors and near medication errors

Medication errors and near medication errors constitute a specific subset of medical events of special interest. They will be summarised, displaying the number of medication errors and the number and percent of patients experiencing the reaction by MedDRA preferred term.

Medication errors and near medication errors will further be listed with patient ID, site, age, preferred term, date of first dose, date of onset, date of arrest, severity, if it is serious or not, relationship to study drug, action, and outcome.

Use of rFXIII other than for prophylactic treatment

Use of rFXIII in patients with congenital FXIII A subunit deficiency, other than for prophylactic treatment will listed with patient ID, site, age and alternative purpose of the administration of rFXIII. A subsection for product doses should be added.

Annualised Bleeding rate

This secondary endpoint comprises the annualised rate of bleeding (covering both treatment requiring and non-treatment requiring), occurring from first study related activity after signing the informed consent to the end of patient's participation in the study.

Annualised bleeding rate will be summarised by cause (spontaneous, traumatic and surgery), therapeutic regimen (prophylactic therapy, on-demand therapy, surgery) severity, site of bleeding, haemostatic treatment administered (product name) and haemostatic response. The ratio between traumatic and spontaneous bleeding rates will further be summarised and listed and graphical displays of the bleeding rates and the referred ratio will be presented by patient, ordering the patients according to increasing values.

Protocol	Date:	02 February 2016	Novo Nordisk
Ct., dr. ID. NN11041 2060	Varaion:	2.0	

 Study ID: NN1841-3868
 CONFIDENTIAL
 Version:
 2.0

 UTN: U1111-1131-1558
 Status:
 Final

 EU PAS No.: ENCEPP/SDPP/3687
 Page:
 47 of 65

Bleeding episodes will further be listed, including information about cause, severity, location, date and time of onset, date and time of arrest, product name, dose, haemostatic response, related concomitant illness and related concomitant medication.

Presentation by previously untreated patients

To the extent that the study enrols patients, who receive their first administration of rFXIII within the scope of the present study, a separate presentation of both primary and secondary endpoints will be conducted for this group of patients.

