4.6 Variables

The study is designed to observe the use of rFXIII in normal clinical practice and hereby further explore the safety profile and effectiveness of rFXIII.

The safety profile of rFXIII will be monitored via collection of data on adverse drug reactions comprising FXIII antibodies, allergic reactions, embolic and thrombotic events and lack of effect. Also, all serious adverse events, all medical events of special interest and all medication errors and near medication errors will be collected.

The effectiveness of prophylactic treatment with rFXIII in patients with congenital FXIII A-subunit deficiency will be measured by collecting data on annualised bleeding rate. Also, data on treatment with rFXIII for other uses than prophylactic treatment in patients with congenital FXIII A-subunit deficiency will be collected.

 Study ID: NN1841-3868
 CONFIDENTIAL
 Version:
 2.0

 UTN: U1111-1131-1558
 Status:
 Final

 EU PAS No.: ENCEPP/SDPP/3687
 Page:
 13 of 65

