9.2.2 Inclusion criteria

- 1. Informed consent obtained before any study-related activities. (Study-related activities are any procedure related to recording of data according to the protocol).
- 2. Able and willing to provide signed informed consent (or patient's legally acceptable representative (LAR) consent, if applicable), as required by local ethics committee, governmental or regulatory authorities.
- 3. Congenital FXIII A-subunit deficiency.
- 4. Actual or planned exposure to the rFXIII.

 Study ID: NN1841-3868
 CONFIDENTIAL
 Version:
 2.0

 UTN: U1111-1131-1558
 Status:
 Final

 EU PAS No.: ENCEPP/SDPP/3687
 Page:
 25 of 65

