9.2.4 Withdrawal criteria

- 1. The patient may withdraw at will at any time.
- 2. The patient's parent or patient's LAR may withdraw the patient at any time.

If antibodies to rFXIII product are detected, the treatment with rFXIII may be continued, interrupted or discontinued at the discretion of the Physician. It is strongly encouraged that the patients remain in the study and have regular follow-up visits for monitoring of antibodies until the level has diminished to below clinical significance or detection limit.

Interruption of treatment with rFXIII or termination of treatment with rFXIII is not a criterion for withdrawal from this study.

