9.7.1 Evaluability of patients for analysis

There will only be a Full Analysis Set in the study, comprising all patients who have entered into the study fulfilling the inclusion and exclusion criteria and having received at least one administration of rFXIII containing product in the study period. The Full Analysis Set will be identical to the Safety Analysis Set.

 Study ID: NN1841-3868
 CONFIDENTIAL
 Version: 2.0

 UTN: U1111-1131-1558
 Status: Final

 EU PAS No.: ENCEPP/SDPP/3687
 Page: 45 of 65

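### The annualised bleeding rate that is to measure rFXIII prophylaxis covers all time from consent to study exit, and no planned breakdown isolates time on rFXIII prophylaxis

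*Protocol*

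**What the plan says.** **Purpose.** Protocol 4.6: "The effectiveness of prophylactic treatment with rFXIII in patients with congenital FXIII A-subunit deficiency will be measured by collecting data on annualised bleeding rate". Sections 4.2 and 7.1 give the rate the same role.

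**Window.** Section 9.7.2.2 defines the rate thus: "This secondary endpoint comprises the annualised rate of bleeding (covering both treatment requiring and non-treatment requiring), occurring from first study related activity after signing". It counts bleeds, treated or not, "occurring from first study related activity after signing the informed consent to the end of patient's participation in the study". The same section applies this window to every secondary endpoint.

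**Who contributes time.** Entry requires only "Actual or planned exposure to the rFXIII" (9.2.2). On leaving, 9.2.4 states: "Interruption of treatment with rFXIII or termination of treatment with rFXIII is not a criterion for withdrawal from this study". The single analysis set (9.7.1) takes eligible patients "having received at least one administration of rFXIII containing product in the study period", and 9.7.2 bases all analyses on that set.

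**Breakdowns.** Besides cause of bleed, the rate is to be summarised by "therapeutic regimen (prophylactic therapy, on-demand therapy, surgery) severity, site of bleeding, haemostatic treatment administered (product name) and haemostatic response" (9.7.2.2).

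**The concern.** The stated purpose and the stated window do not describe the same quantity. The purpose is rFXIII prophylaxis. The window is all participation, whatever the patient was receiving. Three features of the design bring in other time:

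- a patient enrolled on planned exposure contributes time before the first rFXIII dose;
- a patient who interrupts or stops rFXIII, or moves to another FXIII product, goes on contributing;
- a patient given rFXIII once, for example for a bleed, contributes the whole of his or her participation.

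Time off rFXIII need not be spread evenly. Section 9.2.4 lets the physician discontinue rFXIII when antibodies appear and encourages those patients to stay in the study, so such time may gather in the patients with a primary-endpoint event.

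What is at stake is the reading of the study's effectiveness result. A reader of the report, told that the rate measures rFXIII prophylaxis, would attribute to rFXIII bleeds and bleed-free time that belong to no prophylaxis or to another product.

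**Working it through.** **1. Is there a figure to reproduce?** The protocol states no bleeding rate, expected or historical, and no share of time off rFXIII. The only figure that bears on the denominator is the average participation in 9.5, about 4.5 years, or 30 × 4.5 = 135 patient-years for the anticipated minimum of 30 patients. Uniform recruitment over 4 years in a 6-year study gives 6 − 4/2 = 4.0 years, or 120 patient-years. That mismatch is a separate matter, and nothing below rests on it.

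**2. Do the planned breakdowns isolate rFXIII prophylaxis?**

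| Breakdown in 9.7.2.2 | What it separates | What it leaves mixed |
|---|---|---|
| Therapeutic regimen | Prophylaxis from on-demand therapy and surgery, on a natural reading (stratum denominators are not spelled out) | rFXIII prophylaxis and prophylaxis with another FXIII product |
| Haemostatic product name | Bleeds by the drug given to treat them, as recorded under 9.3.4.1 | Prophylactic product; untreated bleeds have no such product, yet count in the rate |

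Other haemostatic products are expected and recorded (9.3, 9.3.5.1). Neither breakdown yields a denominator of time on rFXIII prophylaxis.

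**3. The prophylactic stratum.** Let g be the share of prophylactic time on another product, and let r_on and r_other be the two bleeding rates. The stratum rate is (1 − g) × r_on + g × r_other, which differs from r_on by g × (r_other − r_on). This is zero if the products perform alike, positive if the other product does worse and negative if it does better. The documents give none of the three quantities, so neither sign nor size follows.

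**4. The overall rate, as illustration only.** Let f be the share of participation without protection and r_off the rate in that time. Overall rate = (1 − f) × r_on + f × r_off. Assumed: r_on = 0.15 per year, r_off = 1 or 2 per year.

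| f | r_off = 1 | r_off = 2 | Multiple of r_on |
|---|---|---|---|
| 5% | 0.1425 + 0.05 = 0.193 | 0.1425 + 0.10 = 0.243 | 1.3 to 1.6 |
| 10% | 0.135 + 0.10 = 0.235 | 0.135 + 0.20 = 0.335 | 1.6 to 2.2 |
| 20% | 0.12 + 0.20 = 0.320 | 0.12 + 0.40 = 0.520 | 2.1 to 3.5 |

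The multiple depends heavily on the assumed r_on. At f = 10% and r_off = 2:

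- r_on = 0.05 gives 0.045 + 0.20 = 0.245, or 4.9 times;
- r_on = 0.2 gives 0.18 + 0.20 = 0.38, or 1.9 times.

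If the time off rFXIII is covered by another product with the same rate, say 0.2 and 0.2, the overall rate stays at 0.20 and the multiple is 1.0.

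**5. How much time is plausible?** With 120 patient-years, f = 5%, 10% and 20% mean 6, 12 and 24 patient-years off protection. Lead-in time alone would hardly reach this: if all 30 patients waited one month for a first dose (assumed), the total would be 30/12 = 2.5 patient-years, about 2%. Time after stopping can weigh more in a single patient. Six months is 0.5/2 = 25% of the 2 years (6 − 4) left for the last patient recruited, and 0.5/6 = 8% of a full 6-year participation.

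**The case against.** The study is purely descriptive, and one secondary objective (8.1.2) is effectiveness under routine care. A rate over all participation is a legitimate real-world summary, and 9.7.2.2 does not say which version is the headline. This stands, and it is a reason to keep the full-participation rate. It does not make that rate a measure of rFXIII prophylaxis, which is how 4.6 describes it.

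The regimen breakdown already deals with the largest contrast, protected against unprotected time. This also stands. A reader might infer from the illustration that the effectiveness result will be inflated 1.3 to 3.5 times. The documents do not support that: the figures are assumed, they concern the overall rate only, and on a natural reading on-demand time falls outside the prophylactic stratum.

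Time before rFXIII is probably short. The decision to treat precedes inclusion (9.1.3), prophylaxis is described as once monthly (9.1.4), and patients first exposed in the study get a separate presentation (9.7.2.2). That is fair, but it does not touch time after interruption, stopping or switching.

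Finally, a statistical analysis plan could define person-time within strata. It could add a rate on rFXIII prophylaxis without contradicting the protocol. Making that the endpoint itself would depart from the window the protocol fixes, so the protocol is the right place to settle it.

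**Conclusion.** The point holds in a narrow form. The overall annualised bleeding rate mixes rFXIII prophylaxis, other products and time without prophylaxis. The prophylactic stratum removes the on-demand part but still combines rFXIII with any other prophylactic FXIII product. No planned summary gives bleeds per year on rFXIII prophylaxis, which is what 4.6 says the rate measures.

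The size and direction of the distortion cannot be derived from the documents. It would be negligible if few patients switch or stop, or if other products perform alike; even then, time on another product would be credited to rFXIII. The conclusion about the prophylactic stratum assumes that its denominator is time on a prophylactic regimen, which 9.7.2.2 does not state. The endpoint is secondary and descriptive, so no hypothesis test and no primary result depends on it. The repair is worth making because it is specific and inexpensive.

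**What to change.** In 9.7.2.2, define the rate used for the effectiveness of rFXIII prophylaxis as follows.

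- **Numerator:** bleeds, treated or not, with onset during rFXIII prophylaxis.
- **Denominator:** the sum of the patient's rFXIII prophylaxis intervals. The first starts at the first in-study prophylactic dose, or at consent if the patient is already on rFXIII prophylaxis.
- **Excluded from both:** interruptions, periods on another product and periods without prophylaxis. A single span from first to last dose will not do, because an interruption, or a switch and return, inside it would still count as rFXIII time.
- **Interval rule:** state in advance, by reference to the regimen recorded for the patient, when an interval is taken to have ended. This is a counting rule only and implies nothing about treatment.

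Report the full-participation rate alongside, so that patients who stop remain visible, and state the denominators of the regimen strata.

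The cost is some programming and slightly less person-time. Product, dose and date are already foreseen in the diary, or in the CRF for doses given in hospital (9.3.5.1). The diary, however, is supplied only where it is routine at the clinic, and 9.3 asks for data only if available or performed. Report how much participation time could not be classified by product.

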Treatment in relation to bleeds, surgery and bleeding prophylaxis is currently managed using plasma-derived FXIII freeze-dried products, cryoprecipitate, or fresh-frozen plasma. Desmopressin or antifibrinolytics do not have primary haemostatic effects in patients with homozygous FXIII deficiency⁹.

The rFXIII product

The study medication, rFXIII, is manufactured as an intracellular, soluble protein in a yeast production strain ($Saccharomyces\ cerevisiae$). The purified protein is an rFXIII [A2] homodimer and is freeze dried. Each vial contains 2500 IU and is supplied as a lyophilized powder. The product is to be reconstituted with sterile water and administered intravenously. Further details are available in the approved product information European Summary of Product Characteristics (EU SmPC), United States Physician Information (US PI) or corresponding local prescribing information.

 Study ID: NN1841-3868
 CONFIDENTIAL
 Version:
 2.0

 UTN: U1111-1131-1558
 Status:
 Final

 EU PAS No.: ENCEPP/SDPP/3687
 Page:
 21 of 65

8 Research question and objectives

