9.3.2.2 Bleeding treatment history and history of bleeding episodes

- Current prophylactic treatment and treatment for the last five years. If shorter, for the actual prophylactic period (name of product, dose, dose frequency and duration of prophylaxis (start/stop date)).
- Number of bleeds during prophylaxis treatment in the last 24 months (both treatment required and non-treatment requiring).
- On-demand treatment as reported by the patient.
- Number of treatment requiring bleeding episodes within the last 24 months.
- FXIII product used, and product used for the last five years. If shorter, for the actual ondemand period (name and yearly dose, if available).
- Surgeries within the last 12 months.
- Date of surgery.
- Type of surgery (minor/major and elective/emergency).
- Haemostatic product (name if available and dose).

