9.7.2.1 Primary endpoint

The primary endpoint comprises specific adverse drug reactions in terms of anti-FXIII antibodies, allergic reactions, embolic and thrombotic events and lack of therapeutic effect occurring from first study related activity after signing the informed consent to the end of patient's participation in the study.

The referred specific adverse drug reactions of the primary endpoint (anti-FXIII antibodies, allergic reaction, embolic and thrombotic events and lack of therapeutic effect) will be summarised, displaying the number of reactions and the number and percent of patients experiencing the reaction relevant within system organ class and Medical Dictionary for Regulatory Activities (MedDRA) preferred term. Assessments of anti-FXIII antibodies will be provided by the central laboratory. The endpoint will be presented for all patients as well as by special populations, comprising children, elderly, pregnant and lactating women, and patients with renal insufficiency.

All the specific adverse drug reactions will further be listed with patient ID, site, age, preferred term, date of first dose, date of onset, date of arrest, severity, if it is serious or not, relationship to study drug, action, and outcome.

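### The subgroup called previously untreated patients is defined only by first rFXIII dose in the study, so it pools rFXIII-naive switchers from other FXIII products with patients who never had any.

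*Protocol*

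**What the plan says.** The last part of Protocol section 9.7.2.2 carries the heading "Presentation by previously untreated patients". The sentence beneath it gives the whole definition of the group: "To the extent that the study enrols patients, who receive their first administration of rFXIII within the scope of the present study". For these patients, "a separate presentation of both primary and secondary endpoints will be conducted for this group of patients". Under section 9.7.2.1 the primary endpoint consists of "specific adverse drug reactions in terms of anti-FXIII antibodies, allergic reactions, embolic and thrombotic events and lack of therapeutic effect". The secondary endpoints include the annualised bleeding rate.

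Other sections bear on who can enter this group:

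- Section 7.2, under treatment options: "Treatment in relation to bleeds, surgery and bleeding prophylaxis is currently managed using plasma-derived FXIII freeze-dried products, cryoprecipitate, or fresh-frozen plasma".
- Sections 9.2.2 and 9.2.3: patients need congenital FXIII A-subunit deficiency and actual or planned rFXIII exposure. The single exclusion concerns capacity, willingness and language.
- Section 9.3.2.2: Visit 1 records "Current prophylactic treatment and treatment for the last five years", with product name, and likewise the FXIII product used on demand over five years.
- Sections 9.3.2.3 and 9.3.2.5: Visit 1 also records earlier lack of effect of FXIII-containing products and any history of anti-FXIII antibodies, with type, values and dates.

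No other section of the protocol defines the term previously untreated or ties the Visit 1 history to this subgroup.

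**The concern.** The heading and the definition describe two different populations. Previously untreated means that the patient has had no earlier treatment for the deficiency. First rFXIII in the study means only that the patient is new to this product, whatever FXIII source came before.

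The difference matters most for the endpoints shown. Antibodies and allergic reactions are named first in the primary endpoint, and earlier exposure to FXIII protein bears on how both should be read. Earlier prophylaxis also bears on how a bleeding rate should be read. In a single-arm descriptive study the named tables are the result. A low antibody count under this heading would be taken to describe first exposure to FXIII, although the group may contain people long exposed to it. Conversely, an antibody first acquired on another product could appear under a name implying that the patient had received nothing before rFXIII.

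**Working it through.** The protocol gives no figure to reproduce here. The check is to apply the definition in section 9.7.2.2 to the kinds of patient that the other sections admit.

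| Patient | Eligible under 9.2.2 and 9.2.3? | In the subgroup under 9.7.2.2? | Truly previously untreated? |
|---|---|---|---|
| (a) No FXIII-containing product ever; first rFXIII dose in the study | Yes | Yes | Yes |
| (b) Five years of plasma-derived FXIII prophylaxis; first rFXIII dose in the study | Yes | Yes | No |
| (c) As (b), with earlier anti-FXIII antibodies or lack of effect on record | Yes | Yes | No |
| (d) rFXIII already given before enrolment | Yes | No | No |

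Rows (a), (b) and (c) fall under one heading, which is correct only for row (a).

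**Are rows (b) and (c) realistic?** Section 7.2 says that treatment "is currently managed using plasma-derived FXIII freeze-dried products" or with the other plasma sources. Section 9.3.2.2 sets aside Visit 1 fields for five years of such products, and sections 9.3.2.3 and 9.3.2.5 do so for earlier failures and antibodies. The protocol therefore expects patients with these histories. It does not say how many.

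**What the mixture can do to a result.** The exact two-sided 95% upper limit when no event is seen in n patients is 1 − 0.025^(1/n). The counts below are assumptions: 10 patients with their first rFXIII in the study, no antibodies in any of them, and a varying number who never had another FXIII product.

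| Truly untreated among the 10 | Calculation | Upper limit for the truly untreated |
|---|---|---|
| 10 (no switchers) | 1 − 0.025^(1/10) | 30.8% |
| 5 | 1 − 0.025^(1/5) | 52.2% |
| 2 | 1 − 0.025^(1/2) | 84.2% |
| 0 (all switchers) | no patients | no information |

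In every row the pooled presentation would read 0/10, with an upper limit of 30.8%. What it says about previously untreated patients runs from exactly that to nothing. The protocol plans no intervals for these counts; the limits only show how much the meaning of the same table depends on an undisclosed split.

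**The case against.** The strongest reply is that this is a fault of labelling, not a hidden rule. The one sentence under the heading states the criterion in full. The primary objective in section 8.1.1 concerns reactions associated with rFXIII, and section 7.2 describes rFXIII as a yeast-produced A2 homodimer, so first rFXIII exposure is a sensible grouping even for a switcher. The protocol fixes no table title. Sections 9.7.2.1 and 9.7.3 also list each specific reaction by patient and list the treatment and antibody history, so in about 30 patients most earlier exposure could be traced by hand. How to split a table is commonly left to the statistical analysis plan.

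Much of this stands. The rFXIII-naive grouping is worth keeping, and most of the data needed to interpret it are collected. The reply does not remove the conflict: the protocol states both a name and a rule, and the rule admits patients whom the name excludes. Separate listings do not correct what the subgroup summary would be taken to mean.

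Three stronger readings are tempting but go beyond the text:

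- A reader might infer that most or all patients starting rFXIII will be switchers. Section 7.2 makes switchers likely, but no share is stated, and section 9.1.2 notes that not every diagnosed patient currently needs treatment.
- A reader might infer that switchers have already tolerated FXIII, so that the subgroup is biased towards reassurance. Sections 9.3.2.3 and 9.3.2.5 provide for earlier lack of effect and earlier antibodies, and neither is an exclusion. A patient may have switched because of a problem.
- A reader might infer that patients already on rFXIII at entry must have tolerated it. Section 9.2.2 asks only for actual or planned exposure, and section 9.2.4 lets treatment continue after antibodies are found, at the physician's discretion.

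The lack of a separate table for patients already exposed to rFXIII is not an error either, since they are the complement of the subgroup among all patients.

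**Conclusion.** The point holds as a conflict between the subgroup's name and its definition. As written, section 9.7.2.2 would present patients earlier treated with plasma-derived FXIII, cryoprecipitate or fresh-frozen plasma as previously untreated, for the primary and the secondary endpoints.

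Its size cannot be fixed from the protocol, because the affected share may be anything from none to the whole subgroup. The direction is also open, because the earlier exposure may have been uneventful or may have involved antibodies or lack of effect. The conclusion rests on two assumptions: that at least some patients starting rFXIII in the study had another FXIII-containing product before, which sections 7.2 and 9.3.2.2 support, and that readers will take the heading at its word.

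The consequence is limited to this subgroup. The study is descriptive, so no test is involved, and neither the all-patient results nor the study size changes. The correction should still be made, because it decides what the subgroup can be said to show.

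**What to change.** In section 9.7.2.2, rename the presentation to patients receiving their first rFXIII in the study (rFXIII-naive). Within it, show patients with and without earlier FXIII-containing treatment separately, using the Visit 1 history from sections 9.3.2.2 and 9.3.2.5. Keep the term previously untreated for patients with no known earlier FXIII-containing product, and state beside it that the product history goes back only five years.

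A single yes/no item at Visit 1 on any FXIII-containing product ever received would close the five-year gap. For patients already enrolled it could be filled from the record or by query. It is a useful option, not a necessary part of the correction. Showing patients exposed to rFXIII before entry alongside is likewise optional.

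The cost is a change of wording and one table split, with no new visit, sample or change of treatment. The drawback is that the truly untreated group may be very small or empty. In that case the report should say that the study holds little or no information on such patients.
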